### 9.1.3 Continuous household survey

#### 9.1.3.1 Continuous malaria indicator survey (cMIS)

Community malaria infection prevalence will be evaluated through an ongoing protocol involving participants of all ages, “Malaria Indicator Household Surveys to evaluate the impact of malaria transmission reduction activities in Siaya County, western Kenya: a continuous rotating panel survey”; short title, “Continuous Malaria Indicator Survey (cMIS)” [KEMRI SERU Protocol# 2773; CDC IRB# 6733; LSTM REC# 14.009; PATH RDC# 0777]. The survey will include malaria blood testing by RDT and PCR. The RDT result will dictate malaria treatment in the field, and PCR results will be processed at a later date to estimate the secondary outcome of infection prevalence by PCR. The individual and household questionnaires will capture information about malaria intervention coverage (e.g. LLIN ownership and use), housing characteristics, and household demographic information. The surveys will also measure a set of indicators regarding ATSB knowledge and perceptions.

#### 9.1.3.2 Brief description of cMIS procedures

- Households are randomly selected for household visits

- Staff members administer informed consent
- Staff members administer the cMIS questionnaire on a password protected study tablet, which includes questions about the history of illness, care-seeking, malaria prevention methods and coverage
- Study staff collect blood (250 µL to 1 mL) from a finger- or heel-prick to prepare approximately five blood spots on filter paper and to perform a rapid diagnostic test. If the RDT is positive, the study staff member treats the participant per Kenya Ministry of Health guidelines

#### 9.1.4 Passive case detection

Confirmed malaria case incidence data will be collected from outpatient health facilities, ANC clinics, and from CHVs providing diagnostic testing in the community through the Kenya Ministry of Health. These are routine surveillance data collected by the Ministry of Health and do not include personally identifiable information. Numbers of participants with suspected malaria, tested for malaria (RDT or microscopy), diagnosed with malaria and treated for malaria are recorded in the routine registries collected at these facilities and by CHVs.

The population denominator for incidence calculations will be derived from the house-to-house enumeration and census.

#### 9.1.5 Entomological monitoring

Entomological monitoring activities will include routine indoor and outdoor mosquito collections using CDC UV light traps and human landing catches (HLC), monitoring for insecticide resistance, and ATSB durability.

##### 9.1.5.1 *UV light traps*

1. Twelve intervention area and 12 control area clusters will be randomly selected for entomological monitoring using UV Light traps.
2. Entomological field assistants will receive training in the study methods and procedures for mosquito collections.
3. Informed consent will be administered to the head of household
4. UV light trap collections will be conducted monthly for the duration of the trial. The household sampling frame generated during the census will be used to select a random sample of 10-12 households per cluster.
5. Collections from clusters will be completed in pairs: one intervention and one control cluster pair. If feasible, collections from all 10-12 households in each of the 2 clusters will be completed in one night. If this is not feasible, collections will be completed over two nights from 5-6 households per cluster per night.
6. In each selected household, a UV light trap will be hung at the foot of a bed or sleeping space by the entomology field team between 1700-1800HRS in the evening. The UVLT should be set next to a bed or sleeping space with a net hanging over it. The house owners will be instructed not to touch it until removed by the team the next morning
7. An additional light trap will be set up outdoors
8. In the morning, the entomology field assistants will visit the household, ensure the UVLT is still running and then carefully remove the collection cup to ensure no mosquitoes escape. Mosquitoes will be returned to the KEMRI CGHR laboratory in Kisian or a field laboratory, where mosquitoes will be sorted and processed for further analyses.

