### 6.3.8 Entomological monitoring

#### 6.3.8.1 *Monthly/quarterly mosquito catches*

Entomological data will be collected on a monthly basis from 10-12 households in each of 24 randomly selected study clusters (12 intervention and 12 control; total= 240-288 houses per month). Collection of monthly mosquito catches will use UV light traps. Human landing catches will be performed quarterly in 4 houses in each of 12 randomly selected clusters (6 control and 6 intervention clusters; total = 48 houses per quarter).

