#### 7.6.3 **Other malaria control interventions**

Community-case management of malaria by community health volunteers is an active intervention promoted by the Ministry of Health in this area. In this strategy, community health volunteers test and treat participants encountered in the households who complain of symptoms compatible with

malaria. Additionally, in September 2019, the Kenya Ministry of Health began a phased implementation of GSK's Mosquirix vaccine in children aged 5-17 months of age. Rarieda sub-county was chosen as an initial vaccinating sub-County, whereas Alego-Usonga was not. To control for the impact of RTS,S/AS01 on our study outcomes, we will ensure a balance of clusters between arms in Rarieda and Alego-Usonga sub-Counties. Additionally, we will record the vaccination status of all children <5 years of age from the maternal-child booklet or from vaccination cards. Where available, we will take a photograph of the child's vaccination records. Where not available, we will use maternal recall. The Kenya Division of National Malaria Program (DNMP) does not currently have plans to perform IRS in Siaya County during the trial period. Should IRS be implemented in the trial area during the trial, the study team will monitor timing and coverage of the campaign at a household and cluster level but will not be responsible for regulating or "topping up" IRS should DNMP initiate spraying in the area.

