### 7.8.2 Continuous malaria indicator survey to assess malaria parasite prevalence

#### 7.8.2.1.1 *Main trial*

The continuous malaria indicator survey (cMIS), conducted under a separate protocol, provides adequate power to detect a 30% reduction in the all-age malaria prevalence detected by RDTs per year from 29.0% to 20.3%. The 29% prevalence is based on the observed all-age prevalence in Rarieda sub-county (29%) (representing two-thirds of the study area) and in Alego-Usonga (47.3%), representing one-third of the study area. The 47.3% in Alego-Usonga is based on cMIS data in neighbouring Karemo. The prevalence estimate in Rarieda is reduced from 29% to 27.7% to account for a 50% drop in malaria prevalence in children < 5 years of age who will receive the RTS,S vaccine. Because this age group only represents 13.9% of the population, the anticipated impact of RTS,S on the all-age prevalence in Rarieda is modest. The pooled estimate of the RTS,S adjusted all-age prevalence of 27.7% in Rarieda and 47.3% in Aleg-Usonga is 34.1%. We propose to use a more conservative prevalence of 29% to allow a 15% reduction in malaria prevalence due to annual variations in environmental conditions (e.g. rainfall, temperature) ( $0.85 \times 34.1\% = 29\%$ ). This requires 3,520 participants per year (44 per cluster, including 9 non-responders and 35 responders) (ICC=0.05, power=90%, two-sided alpha=0.05, and assuming 20% non-responders, e.g. refusals, not at home, etc.). The values for the intra-cluster correlation (ICC), parasite prevalence, and non-response rates were estimated from the ongoing cMIS study. Where possible, households that are included in the first year will be excluded in the second year. Over 2-years, and assuming no overlap in participants between the first and second year, a sample size of 88 per clusters (including 18 non-responders and 70 responders) would provide 80% power to detect a 23.7% reduction or 90% to detect a 27.3% reduction (ICC=0.05, alpha=0.05). Similarly, 70 responders per cluster after two years would provide 80% power to detect a 30% reduction if the ICC is 0.091 instead of 0.05, or 90% power if the ICC is 0.064.

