## 8 METHODS: ASSIGNMENT OF INTERVENTIONS

### 8.1 ALLOCATION AND RANDOMIZATION

Restricted randomization will be used to allocate 80 of the 100 baseline clusters to intervention and control arms for the main trial to minimize any imbalance between study arms on key baseline characteristics. The steps to achieve restricted randomization will be conducted by a study team member who is not responsible for trial implementation. The steps are as follows:

1. Establish balance criteria. The factors described in the table below may be considered for suitability as restriction criteria.
2. Generate a list of at least 100,000 randomizations
3. Check randomizations against balance criteria and drop those that do not fit
4. Assess the number of randomizations left. There may be a need to relax criteria and start again if fewer than 10,000 acceptable randomizations remain.
5. Test remaining set of potential randomizations for validity, specifically that all clusters are being independently assigned to study arms (e.g. check that no two clusters are always jointly assigned to the same arm).
6. Randomly choose a randomisation.
7. Flip a coin to determine if arm A or arm B is ATSB or control.
8. Step 6 and 7 to be done in public with community participation.

Table 3: Factors to consider for restricted randomisation

Covariable/ endpoint	Restriction criteria	Data source	Analytic method
Malaria disease incidence	The difference in mean clinical case incidence between trial arms (size of difference to be assessed when data are available)	Baseline cohort	The difference in disease incidence of cluster summaries between study arms
Bednet use	The difference in mean proportion of persons slept under any net night before survey between trial arms $\leq 5$ percentage points	Baseline survey	The difference in means of cluster summaries of the proportion of persons of all ages slept under any net night before survey between arms

Population	The total population size of the larger trial arm is no more than 10% larger than the smaller arm	Enumeration datasets	Sum(pop size of clusters Arm large)/Sum(Pop size of clusters arm Small) less than 1.10
RTS,S/AS01 vaccinating area	Number of clusters in intervention and control arm balanced by vaccinating or non-vaccinating areas for RTS,S/AS01	Kenya National Vaccinations and Immunizations Programme (NVIP)	N in Arm A == N in Arm B

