#### 9.1.5.2 *Human landing catches*

1. Six clusters not included in the monthly UVLT sampling will be randomly selected from each arm, and within each cluster, four households will be purposively selected for quarterly indoor and outdoor mosquito collections using human landing catches. Each household will participate in this collection for two nights.
2. Selected households will be visited in advance of the collection night and provided information about the study. Informed consent will be sought from the head of the household or his/her representative.
3. A team of 6 collectors will be consented per house. They will be divided into pairs, and each pair will work up to a 6-hour shift during the night. Collections will begin at 5 pm in the evening and continue through 11 am the following morning.
4. Collectors will work for 45 minutes each hour and then take a 15-minute break to rest, take food if necessary and prepare for the next hour of collection. Each pair of collectors will work for 6 hours before a new shift will take over.
5. Prior to the HLC, collectors will be trained to properly aspirate mosquitoes, ideally before they are bitten, and will have ample time during training to practice the technique so as to minimize bites during collections.
6. The collectors will sit in fixed spots, one inside the house and one outside at least 5m away from the house. They will then expose their lower legs, and using a torch (flashlight) and a mouth aspirator, they will collect mosquitoes that land on their lower legs. Collected mosquitoes will be placed in individually labelled paper cups with a separate cup for each hour of indoor collection and outdoor collections.
7. Mosquitoes will be returned to the KEMRI CGHR laboratory in Kisian or a field laboratory in the study area where mosquitoes will be sorted and processed for further analyses.

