#### 9.4.5 **Analysis of entomological data**

Mosquito densities will be analysed by Poisson or negative binomial regression using generalized estimating equations to adjust for correlated observations at the cluster level. Separate models will be done for each species where adequate numbers have been collected. All models will assume an auto-regressive correlation structure where the degree of correlation decreases with increasing time between collections. Models will include potential confounders such as the use of LLINs, recent house spraying, the presence of open eaves, and climatic factors. Logistic regression models will be used to compare the impact of ATSBs on binary outcomes such as the sporozoite rates, parity rates, the proportion of mosquitoes with three or more ovarian dilatations, or the proportion of outdoor biting. The logistic regression models will adjust for correlated observations at the cluster level using assuming an auto-regressive correlation structure.

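### The entomology clusters are drawn at random with no sub-county condition, so the sub-county balance enforced for all 80 clusters is not guaranteed in the entomology comparison

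*Protocol*

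**What the plan says.** **Selection.** For light traps, section 9.1.5.1 states "Twelve intervention area and 12 control area clusters will be randomly selected for entomological monitoring using UV Light traps". For landing catches, section 9.1.5.2 states "Six clusters not included in the monthly UVLT sampling will be randomly selected from each arm". Section 6.3.8.1 gives the resulting workload: "12 intervention and 12 control; total= 240-288 houses per month" and "6 control and 6 intervention clusters; total = 48 houses per quarter". Light-trap collections run in pairs of one intervention and one control cluster, but the pair is not required to come from the same sub-county.

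**Balance in the main allocation.** Section 7.6.3 says "we will ensure a balance of clusters between arms in Rarieda and Alego-Usonga sub-Counties", and gives the RTS,S/AS01 roll-out as the reason. The matching row of Table 3 (section 8.1) reads "Number of clusters in intervention and control arm balanced by vaccinating or non-vaccinating areas for RTS,S/AS01", with equal counts required. Another row of Table 3 asks for equal numbers of entomology clusters in the two arms, but says nothing about where those clusters lie.

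**How the areas compare.** Section 7.8.2.1.1 reports the "observed all-age prevalence in Rarieda sub-county (29%) (representing two-thirds of the study area) and in Alego-Usonga (47.3%), representing one-third of the study area". It adds that the second figure comes from survey data in neighbouring Karemo.

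**Analysis.** Section 9.4.5 says "Models will include potential confounders such as the use of LLINs, recent house spraying, the presence of open eaves, and climatic factors". Sub-county is not among the examples.

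**The concern.** The allocation balances sub-county over 40 clusters per arm. The entomology comparison uses only 12 per arm for light traps and 6 for landing catches. A random draw of that size, with no sub-county condition, will often give the two arms different mixes of Rarieda and Alego-Usonga clusters.

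If vector density, sporozoite rate or entomological inoculation rate differs between the areas, a chance excess of one area in one arm moves the estimated effect. When the mix happens to be even, the sub-county difference still sits in the between-cluster variance unless the model removes it.

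These outcomes are the trial's direct evidence on transmission. Section 10.4.2.8 also uses the arm trends at one year: an apparent absence of entomological effect sets off a full review of trial procedures, coverage and data quality.

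**Working it through.** **1. The plan's own counts.** Light traps: 24 × 10 = 240 and 24 × 12 = 288 houses per month. Landing catches: 12 × 4 = 48 houses per quarter. All reproduce.

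**2. Inputs for the draw.** There are 40 clusters per arm (section 2.4.1). The protocol gives no cluster count by sub-county. If clusters follow the two-thirds area share in section 7.8.2.1.1, K = 40 × 2/3 ≈ 27 per arm are in Rarieda. This is an assumption, and K is varied from 20 to 30.

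**3. Distribution of the imbalance.** In each arm the number of Rarieda clusters among n drawn is hypergeometric: P(X = i) = C(27, i) · C(13, n − i) / C(40, n). The difference D between two independent arms has mean 0 and variance 2 · n · (27/40) · (13/40) · (40 − n)/39. For n = 12 the SD is √3.78 = 1.94; for n = 6 it is √2.30 = 1.51. Drawing the landing-catch clusters from those left after the light-trap draw does not alter their marginal distribution.

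| | Light traps (n = 12) | Landing catches (n = 6) |
|---|---|---|
| P(equal Rarieda counts), K = 27 | 0.20 | 0.26 |
| P(gap of 2 or more), K = 27 | 0.44 | 0.32 |
| P(gap of 3 or more), K = 27 | 0.20 | 0.09 |
| P(gap of 2 or more), K = 20 to 30 | 0.40 to 0.47 | 0.28 to 0.35 |

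With equal numbers per sub-county in each arm, the gap is zero by construction.

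**4. Shift in the density ratio.** The documents give no vector density by sub-county. As a stand-in, take the prevalence ratio R = 47.3/29 = 1.63, with a range of 1.3 to 2.0. A gap of g clusters out of n multiplies the ratio of geometric means by R^(−g/n) when the excess lies in the lower-density area, and by the inverse in the other direction.

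- Light traps, g = 2: 1.63^(−2/12) = 0.92, a shift of about 8%. At R = 1.3 it is 0.96 (4%) and at R = 2.0 it is 0.89 (11%).
- Landing catches, g = 2: 1.63^(−2/6) = 0.85, a shift of about 15% (8 to 21%).
- Check on arithmetic means, light traps split 9 v 7: (9 + 3 × 1.63)/(7 + 5 × 1.63) = 13.89/15.15 = 0.92.

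**5. Precision.** Section 7.8.3 gives 12 clusters per arm, 10 collections per cluster, ICC 0.38, 80% power and a 50% reduction, but no mean or SD, so the variance has to be back-calculated.

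- Design effect: 1 + 9 × 0.38 = 4.42. Effective n per arm: 120/4.42 = 27.1.
- Detectable standardised difference: (1.96 + 0.84) × √(2/27.1) = 0.76. Implied log-scale SD: ln 2/0.76 = 0.91, so total variance ≈ 0.83.
- Between-cluster variance: 0.38 × 0.83 ≈ 0.316. Within-cluster contribution to a cluster mean: 0.62 × 0.83/10 ≈ 0.051. Variance of a cluster mean ≈ 0.367.
- Sub-county part: (2/3)(1/3)(ln 1.63)² = 0.053.
- Interval width after removing it: √((0.367 − 0.053)/0.367) = 0.925, or about 7.5% shorter. R = 1.3 gives 2% and R = 2.0 gives 16%.

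**The case against.** A random subsample of randomised clusters has an expected sub-county difference of zero, so the comparison is not biased, and a correct cluster-level standard error already covers the imbalance. This stands. A reader might infer that the balance is lost, or that the entomology estimates are invalid. The documents support neither reading: the balance is not guaranteed, and the cost is efficiency.

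The sub-county balance was introduced because of vaccine effects on human outcomes, not to equalise vector density. This also stands. The 1.63 is a ratio of human infection prevalences, and one of its two terms is a proxy from Karemo, so it shows only what a difference of that size would do.

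The absence of stratification is read from silence. Random selection does not exclude stratified selection, and the Table 3 row on planned entomology suggests that the clusters may be marked before allocation. In that case the 44% and 32% need not apply as computed. But no passage carries the sub-county condition into the subsample under either mechanism.

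The covariate list in section 9.4.5 is open, so sub-county could be added later. That would recover much of the precision, but it would not change which clusters were drawn.

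Finally, an 8% shift is small beside the 50% reduction used for sample size. That is fair for the light traps. The landing catches, with six clusters per arm, are more exposed.

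**Conclusion.** The point holds as an avoidable inefficiency in a secondary comparison. The stated selection has no sub-county condition, so a balance that the allocation enforces for 80 clusters is not guaranteed for the 24 light-trap and 12 landing-catch clusters. With about 27 of 40 clusters per arm in Rarieda and independent draws in each arm, a gap of two or more arises in about 44% and 32% of draws respectively.

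The consequence for density depends on the assumed ratio between sub-counties. At 1.63 (1.3 to 2.0), a two-cluster gap shifts the light-trap ratio by about 8% (4 to 11%), and removing sub-county variance shortens the intervals by about 7.5% (2 to 16%). If vector density does not differ between the sub-counties, the density comparison loses nothing.

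The primary cohort comparison uses all 80 clusters and is unaffected. The case for acting is that the improvement is free.

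**What to change.** 1. In sections 6.3.8.1, 9.1.5.1 and 9.1.5.2, state that entomology clusters are selected at random within sub-county, with the same number per sub-county in each arm and roughly in proportion to the final cluster counts. If two-thirds of the clusters are in Rarieda, that would be, for example, 8 + 4 per arm for light traps and 4 + 2 per arm for landing catches. The quotas should be set once the 80 clusters are known.
2. If the entomology clusters are to be marked before allocation, put the same per-sub-county condition in the Table 3 entomology row.
3. Form the intervention-control collection pairs within sub-county.
4. Include sub-county as a fixed term in the section 9.4.5 models.

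The cost is a sentence or two in the selection procedure and one model term, which uses one degree of freedom. No clusters, traps or staff are added.

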#### 9.1.5.2 *Human landing catches*

1. Six clusters not included in the monthly UVLT sampling will be randomly selected from each arm, and within each cluster, four households will be purposively selected for quarterly indoor and outdoor mosquito collections using human landing catches. Each household will participate in this collection for two nights.
2. Selected households will be visited in advance of the collection night and provided information about the study. Informed consent will be sought from the head of the household or his/her representative.
3. A team of 6 collectors will be consented per house. They will be divided into pairs, and each pair will work up to a 6-hour shift during the night. Collections will begin at 5 pm in the evening and continue through 11 am the following morning.
4. Collectors will work for 45 minutes each hour and then take a 15-minute break to rest, take food if necessary and prepare for the next hour of collection. Each pair of collectors will work for 6 hours before a new shift will take over.
5. Prior to the HLC, collectors will be trained to properly aspirate mosquitoes, ideally before they are bitten, and will have ample time during training to practice the technique so as to minimize bites during collections.
6. The collectors will sit in fixed spots, one inside the house and one outside at least 5m away from the house. They will then expose their lower legs, and using a torch (flashlight) and a mouth aspirator, they will collect mosquitoes that land on their lower legs. Collected mosquitoes will be placed in individually labelled paper cups with a separate cup for each hour of indoor collection and outdoor collections.
7. Mosquitoes will be returned to the KEMRI CGHR laboratory in Kisian or a field laboratory in the study area where mosquitoes will be sorted and processed for further analyses.
8. Collectors will be provided with mefloquine 250 mg weekly for prophylaxis, starting two weeks prior to the HLCs as per manufacturer guidelines. Research has shown that with proper prophylaxis, participants in human landing catch collections are at a reduced risk of malaria infection compared to non-participants living in the same community.[20] To further minimize risk to field workers, they will be instructed to wear long-sleeve shirts during the collections to prevent mosquitoes from landing and biting them on the arms (only the legs are exposed for the collections). Collectors will also be provided with free malaria testing and treatment if they become ill during the course of the HLCs and for up to 4 weeks after.

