### 7.3.4 Eligibility criteria for households for entomological monitoring

#### 7.3.4.1 *Inclusion criteria households for entomological monitoring*

1. Household located within the core area of the cluster
2. Head of household or his/her representative is at least 18 years of age
3. Written informed consent for the collection of entomological data by the head of household or representative

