## 8.2 BLINDING

Allocation of study arms will not be blinded to the participants, the deliverers of the intervention, or the main investigators. Sham ATSBs will not be deployed in control areas because it is logistically not feasible to produce the number of ATSB stations needed for both intervention and control arm. The potential for bias among operator-dependent mosquito catches (indoor and outdoor aspirations) will be minimized using a standardized protocol. Additionally, the potential for bias in mosquito catches using CDC light traps is very low. The potential for changes in human behaviour affecting malaria control intervention coverage, namely LLIN use, will be minimized through comprehensive community engagement and communications. LLIN use will be promoted in intervention and control areas. Additionally, study teams will monitor LLIN use in intervention and control areas to document changes throughout the life of the study. Laboratory processing of mosquito and human blood specimens will be blinded.

To further minimize bias, we will use an objective primary outcome measure and mask all laboratory staff to the treatment assignment of individual participants. The trial statistician will also be blinded regarding the allocation arm when the statistical analysis plan is developed and the analytical syntax is written, which will be validated and completed using dummy randomization codes. The actual

allocation will only be provided to the study team after locking the database and approval of the statistical analysis plan by the independent DSMB before they review any trial results.

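### Human-landing-catch households are chosen purposively, with no stated criterion or masked selector, in an open-label trial, so between-arm landing-catch comparisons can reflect which houses were picked

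*Protocol*

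**What the plan says.** Section 9.1.5.2 of the protocol draws the landing-catch clusters at random: "Six clusters not included in the monthly UVLT sampling will be randomly selected from each arm". The households inside those clusters are handled differently: "four households will be purposively selected for quarterly indoor and outdoor mosquito collections using human landing catches". The section does not say what the choice is based on, who makes it, when it is made, or whether the same houses return each quarter. Section 6.3.8.1 gives the size: "6 control and 6 intervention clusters; total = 48 houses per quarter".

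For light traps, section 9.1.5.1 states: "The household sampling frame generated during the census will be used to select a random sample of 10-12 households per cluster".

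The eligibility rules in section 7.3.4 apply to entomological households generally. They require an adult head or representative, written consent, someone sleeping there on the night, and this location: "Household located within the core area of the cluster". They define which houses may be used, not which are taken.

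Section 8.2 says: "Allocation of study arms will not be blinded to the participants, the deliverers of the intervention, or the main investigators". There are no sham stations in control clusters. On field bias it says: "The potential for bias among operator-dependent mosquito catches (indoor and outdoor aspirations) will be minimized using a standardized protocol". Section 9.4.5 compares arms on mosquito densities and on binary outcomes that include "the proportion of mosquitoes with three or more ovarian dilatations, or the proportion of outdoor biting".

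**The concern.** Randomising clusters protects a comparison of houses only if the houses within clusters are sampled in the same way in both arms. A random draw ensures this in expectation. An unexplained choice made where the arm is known does not. Bait stations hang on outside walls, so anyone visiting a cluster can see its arm.

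Landing catches are the only collections made hour by hour on people, indoors and outdoors. They bear directly on early-evening and outdoor biting, which is the stated reason for developing ATSBs. If the houses picked in one arm tend to be easier to reach, better built, nearer to animals or further from breeding sites than those picked in the other, the difference would be read as an effect of the intervention. Collecting on more nights in houses chosen this way would make the estimate more precise without removing the bias. The same protocol already holds a census frame and uses it for random selection in the neighbouring procedure.

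**Working it through.** **Size of the component.** From section 6.3.8.1: 12 clusters × 4 houses = 48 houses per quarter, which reproduces the stated total. Per arm this is 6 × 4 = 24 houses per quarter. If new houses were chosen each quarter for two years, up to 24 × 8 = 192 per arm could contribute. If the same houses returned, it would be 24. The protocol does not say which.

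**Does anything else in the protocol govern the choice of house?**
- Section 6.3.8.1: the random selection mentioned there is of clusters, not houses.
- Section 7.3.4: sets eligibility only.
- Section 8.1, Table 3: balances the number of entomology clusters across arms, not house choice.
- Section 8.2: a standardised protocol addresses how mosquitoes are caught, not where.
- Section 9.4.5: the density models include LLIN use, recent spraying, open eaves and climate. These remove measured differences in those features. The sentences on the logistic models, which cover outdoor biting, mention only correlation within clusters.
- Section 9.1.5.2: landing-catch clusters are outside the monthly light-trap sample, so that sample offers no randomly drawn houses in the same cluster as a check.

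Nothing found overrides the purposive choice.

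**How a difference in chosen houses would act on a density ratio.** The protocol gives no effect size, variance or power for landing catches, so there is no planned figure to reproduce here. The relation is

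observed ratio = true ratio × (a ÷ c),

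where a and c are the natural densities in the chosen ATSB-arm and control-arm houses, each relative to its cluster average. All values of a and c below are assumptions.

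| a | c | true ratio | observed ratio |
|---|---|---|---|
| 1.00 | 1.00 | 1.00 | 1.00 |
| 0.90 | 1.00 | 1.00 | 0.90 |
| 0.80 | 1.00 | 1.00 | 0.80 |
| 0.70 | 1.00 | 1.00 | 0.70 |
| 0.90 | 1.10 | 1.00 | 0.90 ÷ 1.10 = 0.82 |
| 0.90 | 1.10 | 0.70 | 0.70 × 0.90 ÷ 1.10 = 0.57 |
| 1.00 | 0.90 | 0.70 | 0.70 ÷ 0.90 = 0.78 |

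The first row shows that purposive choice alone creates no bias; it must differ between arms. The last row shows that it can also hide an effect.

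**The proportion biting outdoors behaves differently.** With indoor catch I and outdoor catch O, the proportion is O ÷ (I + O). If the chosen houses have a factor k fewer mosquitoes both indoors and outdoors, it becomes kO ÷ (kI + kO) = O ÷ (I + O), which is unchanged. It shifts only if house choice alters the indoor-outdoor balance. For example, if only the indoor catch is scaled by k, it becomes O ÷ (kI + O). The ratios in the table therefore do not carry over to this outcome.

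**After the change.** A random draw of four houses per cluster keeps the size at 12 × 4 = 48 houses per quarter.

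**The case against.** Much can be said for the plan. The clusters are drawn at random. The primary outcome, clinical malaria in the cohort, does not depend on landing catches, and section 7.8.3 sizes the entomology on light traps. Those traps run indoors and outdoors in randomly drawn houses in 24 clusters, so the density evidence does not rest on landing catches. Section 9.2.4 records roof, walls, eaves, nets, spraying, cooking, coils and animals, and section 9.4.5 adjusts the density models for some of these. Hosting is demanding: six collectors per house, from 5 pm to 11 am, on two nights. Some practical selection is understandable.

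These points stand. They limit the importance of the problem and part of its size, but they do not close it. Unmeasured features remain, and the protocol does not name the covariates for the outdoor-biting model. Practical needs can be met by stated conditions applied equally in both arms.

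A reader might infer more than the protocol supports:
- That section 8.2 overlooks landing catches. It need not: collectors use mouth aspirators indoors and outdoors, so its reference to aspirations can be read to include them. What survives is that standardising the catch does not standardise the choice of house.
- That only 24 houses per arm carry the whole comparison. That is a per-quarter figure.
- That staff will knowingly choose by arm. The protocol does not say who picks the houses. Knowledge of the arm is an inference from the open-label design and the visible stations.

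**Conclusion.** The point holds as a weakness in a secondary component that is cheap to correct. As written, the protocol allows house selection by people who know the arm, and no other provision prevents it. Between-arm landing-catch results can therefore reflect the choice of house as well as the intervention.

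The size and direction of any bias cannot be derived from the documents. The range of 0.90 to 0.70 for a true density ratio of 1.00 rests wholly on an assumed 10% to 30% difference in natural density between the houses chosen in the two arms, before any covariate adjustment. It is an illustration for densities, not an estimate, and says nothing about the size of any shift in the proportion biting outdoors. Nor does the protocol support reading this as a threat to the primary endpoint, or as evidence that the landing-catch results will be biased. If selection does not differ between arms, there is no bias.

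This is not a matter to leave to the statistical analysis plan. House sampling is a field procedure that the protocol itself fixes, and analysis can adjust only for what was measured.

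**What to change.** In section 9.1.5.2, item 1, replace the purposive choice with wording such as: in each selected cluster, households are approached in order from a randomly ordered list of eligible core-area households in the census frame until four have agreed. A household is skipped only for refusal or for practical hosting conditions that are fixed in advance and identical in both arms. Each skip and its reason is recorded and reported by arm.

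If the investigators need to keep a purposive element, the protocol should state the criteria, apply them identically in both arms, and have the houses chosen by someone masked to arm or before allocation is known.

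The cost is one changed sentence and one random list per cluster from a frame already in use for light traps. The number of houses stays at 48 per quarter. The downside is some extra visits when a listed house refuses or cannot host the collectors.
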